### 6.3 Laboratory Data

Clinical laboratory evaluations include:

- Hematology: hemoglobin, hematocrit, red blood cell count, white blood cell count with differential, and platelets
- Serum Chemistry: sodium, potassium, chloride, bicarbonate, calcium, glucose, BUN (urea), serum creatinine, uric acid, ALT, AST, alkaline phosphatase, LDH, total protein, albumin, total bilirubin, direct bilirubin, indirect bilirubin, CPK (with fractionation, if available)
- Lipid Panel: Cholesterol, LDL, HDL, triglycerides (screening only)
- Estimated glomerular filtration rate (eGFR) using the estimated MDRD formula will be calculated and reported by the central lab at each visit that the clinical laboratory test is collected.
- Urinalysis: pH, specific gravity, protein, ketones, nitrites, urobilinogen, leukocyte esterase, protein, glucose, microalbuminuria, and blood. If blood, protein, or leukocytes are positive, reflex to microscopic examination.
- Urine drug screen: for drugs of abuse

Clinical laboratory values will be expressed using both Standard US units and SI units. Tabulations, listings, and graphics will be provided to show the data in both systems. The observed value and change from baseline will be summarized for select continuous laboratory parameters. In addition, shift tables (low, normal, high) will be presented. For AST and ALT, the shift tables will use the categories: Normal, >ULN, >3x ULN, and >5x ULN. In the event of repeat values from the same visit, the non-missing value closest to the target date for the visit will be used. In the case of a tie, the latest record will be used.

All laboratory data will be provided in data listings. Additional listings will be presented for all abnormal laboratory values.

On-study laboratory abnormalities are those with an assessment date after the date/time of first dose of study drug and within 30 days after the last dose of study drug.

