1.3.4 Clinical Adverse Event Profile

To date, 7 clinical studies have been completed in healthy volunteers and migraineurs that inform PK, metabolic interactions, safety, tolerability and efficacy. In total, the current data suggests a favorable benefit-risk profile for rimegepant in the acute treatment of migraine attacks. Efficacy was established in Study CN170003, and the overall database suggests a favorable safety profile. Clinical experience with rimegepant has also allowed the characterization of safety and tolerability at substantial multiples of the intended therapeutic exposure and intended frequency of use. Rimegepant has been assessed in single doses up to 1500 mg and in multiple doses from 75 mg to 600 mg with 14-days of dosing (including 300 mg twice daily), where the higher doses yielded exposures more than 60 times greater in AUC and 30 times higher in C_{max} as compared to the mean therapeutic exposure of a single 75 mg dose. These high exposure multiples were generally well tolerated and safe.

CCI

CCI

Rimegepant appears to be generally safe and well tolerated in humans when given as single oral doses up to the maximum dose of 1500 mg and multiple oral doses up to the maximum daily dose of 600 mg for 14 days. Please refer to the Investigators Brochure for a summary of the clinical safety profile.

The primary identified AE of interest is potential change in liver functions tests. Investigators must carefully monitor routine liver functions tests (ALT, AST, total bilirubin, and ALP) and potentially liver related symptoms and signs. Clinicians should also monitor changes in hematology and other laboratory measures. Please refer to the current Investigators Brochure for further information regarding the clinical safety profile of rimegepant.

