4.3.4 End of Treatment (7 days after Treatment)

Patients will return to the study site within 7 days of study treatment (+2 days) for review of the eDiary assessment of medication compliance, and monitoring of tolerability and safety (including vital signs, laboratory tests, and electrocardiography). If a patient has NOT experienced a migraine headache of sufficient severity within 45 days after randomization, he or she will be withdrawn from the trial and instructed to return unused study medication and eDiary to the study center.

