8.1.5 Potential Drug Induced Liver Injury (DILI)

Wherever possible, timely confirmation of the initial liver-related laboratory abnormalities should occur prior to the reporting of a potential DILI event. All occurrences of potential DILIs, meeting the defined criteria, must be reported as SAEs as per Section 8.1.2.

Potential drug induced liver injury is defined as:

1. Aminotransferases (AT) (ALT or AST) elevation > 3 times the upper limit of normal (ULN)

AND

2. Total bilirubin (TBL) > 2 times ULN, without initial findings of cholestasis (elevated serum alkaline phosphatase)

AND

3. No other immediately apparent possible causes of AT elevation and hyperbilirubinemia, including but not limited to, viral hepatitis, pre-existing chronic or acute liver disease, or the administration of other drug(s) known to be hepatotoxic.

If any potential DILI is identified and meets the criteria above, the Biohaven Medical Monitor (or designee) should immediately be contacted for further instruction on dosing adjustments and whether the patient must discontinue from the trial and appropriate follow up requirements.

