**Table 6: Evaluation Intervals for Efficacy Analysis**

Evaluation	Protocol-Specified Interval	Analysis-Specified Interval
Screening Phase		
Screening	Day -28 to Day -3	Day -40 to Day -3
Acute (Randomization) Phase		
Baseline (Randomization)	Day 1	Day -2 to 1
Onset of Migraine	Day 1 to 45	Day 1 to 45
15, 30, 45, 60, 90 minutes post-dose	Time of Dose + 15, 30, 45, 60, and 90 minutes	Time of Dose + 15, 30, 45, 60, and 90 minutes (as captured in eDiary)
2 hours post-dose	Time of Dose + 2 hours	Time of Dose + 2 hours (as captured in eDiary)
8 hours post-dose	Time of Dose + 8 hours	Time of Dose + 8 hours (as captured in eDiary)
24 hours post-dose	Time of Dose + 24 hours	Time of Dose + 24 hours (as captured in eDiary)
48 hours post-dose	Time of Dose + 48 hours	Time of Dose + 48 hours (as captured in eDiary)
End of Treatment Visit	Time of Dose + 7 days	Time of Dose + 2 to 21 days

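### Laboratory shift tables take the repeat value closest to the visit target, so an abnormal result drawn before Day 7 can be replaced by a later repeat; outside the main liver thresholds no other summary table keeps it

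*SAP*

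**What the plan says.** SAP 6.3 (Laboratory Data) plans observed and change-from-baseline summaries and shift tables. Where a visit has more than one value: "In the event of repeat values from the same visit, the non-missing value closest to the target date for the visit will be used". It adds: "In the case of a tie, the latest record will be used". For transaminases: "For AST and ALT, the shift tables will use the categories: Normal, >ULN, >3x ULN, and >5x ULN". The section gives no target date for laboratory visits. It defines on-study laboratory abnormalities as those assessed after the first dose and within 30 days of the last dose.

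The protocol's Schedule of Assessments has one scheduled post-dose laboratory draw, at the End of Treatment Visit. Protocol 4.3.4 has patients return within 7 days of treatment, with a two-day allowance. SAP Table 6 gives the protocol interval as "Time of Dose + 7 days" and the analysis interval as "Time of Dose + 2 to 21 days", but the table is titled for efficacy analysis.

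SAP Appendix 1 marks the hematology (14.4.3), serum chemistry (14.4.4) and transaminase (14.4.6) shift tables as topline. It also marks as topline the liver toxicity summary (14.4.7), the eDISH plot and the potential drug-induced liver injury listings. The listings of all abnormal values (16.2.10.7) are not topline. Protocol 9.1 names laboratory abnormalities among the endpoints tabulated as unique subjects with an event.

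**The concern.** Repeat draws are often made because the first value was abnormal. For liver tests Protocol 8.1.5 asks, where possible, that "timely confirmation of the initial liver-related laboratory abnormalities should occur prior to the reporting of a potential DILI event". With only one scheduled post-dose draw, a patient who comes back early and is then re-tested may contribute the repeat, and not the value that prompted it, to the shift tables. When that happens the tabulated result tends to move toward normal, and whether it happens depends on how early the patient returned.

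At stake is the descriptive laboratory safety picture, part of which is topline. Clinically relevant laboratory abnormalities are part of the safety objective in both documents. No efficacy result is affected.

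**Working it through.** **Inputs.** Target T = Day 7 and visit interval Days 2 to 21 (SAP Table 6); closest value, ties to the later record (SAP 6.3); first draws on Days 2 to 9 (upper end from Protocol 4.3.4, lower end from Table 6). The documents give no distribution of visit or repeat dates, so the gap from first draw to repeat and the equal weighting of day-pairs are assumptions.

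**Rule.** Let the first draw be on day d and the repeat on a later day r. The repeat is used when |r − 7| ≤ |d − 7|. For d < 7 this means r ≤ 14 − d. For d ≥ 7 no later-day repeat qualifies. A same-day repeat is a tie, so the later record is used whatever the day.

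| First draw | Repeat days that replace it | Gaps 1–7 days | Repeats to Day 21 |
|---|---|---|---|
| Day 2 | 3–12 | 7 of 7 | 10 of 19 |
| Day 3 | 4–11 | 7 of 7 | 8 of 18 |
| Day 4 | 5–10 | 6 of 7 | 6 of 17 |
| Day 5 | 6–9 | 4 of 7 | 4 of 16 |
| Day 6 | 7–8 | 2 of 7 | 2 of 15 |
| Days 7–9 | none | 0 of 21 | 0 of 39 |
| Total | | 26 of 56 (46%) | 30 of 124 (24%) |

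The result depends strongly on when patients return. On the 7-day grid, 14 of the 26 replacements come from first draws on Days 2 and 3. First draws on Days 6 to 9 give 2 of 28 (7%).

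**Other targets.** With a repeat 3 days after the first draw, the first draws replaced are Days 2–3 if T = 5, Days 2–5 if T = 7 and Days 2–7 if T = 9. The mechanism does not depend on Day 7 exactly.

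**Illustrations (hypothetical values).**
- ALT is 4x ULN on Day 4 and 1.8x ULN on Day 9. The distances are 3 and 2, so Table 14.4.6 shows >ULN, not >3x ULN. Table 14.4.7 still counts the subject above 3x ULN.
- A neutrophil count is low on Day 4 and normal on Day 8. The distances are 3 and 1, so Table 14.4.3 shows normal, and no other laboratory table shows the low value.
- A first draw on Day 7 with a repeat on Day 10 gives distances 0 and 3. The first value stays.

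**What else would show a replaced value.**

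| Abnormality | Other summary output |
|---|---|
| ALT or AST >3x ULN | Table 14.4.7 (any post-randomization value); liver injury listing; eDISH (maximum ALT) |
| Bilirubin >1x ULN | Table 14.4.7; eDISH (maximum); liver injury listing if >2x ULN |
| ALP >1.5x ULN | Table 14.4.7 |
| ALT or AST between 1x and 3x ULN | No stand-alone row; SAP 6.3.1 plans a row for elevation combined with certain AEs |
| Hematology, non-liver chemistry | None; only the non-topline listings of abnormal values |

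**The case against.** The strongest reply has four parts.

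1. **Liver signals are protected.** The liver table counts any post-randomization elevation above its thresholds, eDISH uses maxima, and the liver injury listings cover ALT or AST above 3x ULN or bilirubin above 2x ULN at any time. All are topline. This stands. A reader might infer that the rule hides a liver signal; the documents do not support that. Tables 14.4.6 and 14.4.7 can differ for one subject because the first is by visit and the second is any-time.

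2. **Abnormalities that matter become AEs.** Protocol 8.2.2 requires clinically significant laboratory results, and those needing corrective therapy, to be recorded as AEs or SAEs, and the AE tables count them however brief. This also stands, but it depends on investigator judgment and does not supply the tabulation that Protocol 9.1 describes.

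3. **Key premises are inferred.** Day 7 and the Day 2 to 21 interval come from a table titled for efficacy, and nothing says that an unscheduled draw on another date belongs to the same visit. If it does not, the rule never reaches it. Against this, a distance-to-target rule can separate repeats only if they fall at different distances, so the reading is natural. The ambiguity is itself a gap. Further, Protocol 8.1.5 asks for confirmation of liver abnormalities only. For hematology Protocol 1.3.4 says just that "Clinicians should also monitor changes in hematology and other laboratory measures", so prompted repeats of non-liver tests are plausible but not required by these sections.

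4. **The rule is pre-specified, blind to the result and the same in both arms.** That stands. A reader might infer a bias in favor of rimegepant, but nothing in the documents points to arm-specific selection. Early first draws may also be uncommon, since the visit is described as 7 days after dosing.

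**Conclusion.** The point holds in a limited form. Provided Day 7 is the target and a repeat inside Days 2 to 21 belongs to the same visit, an abnormal first value drawn before Day 7 can be displaced in Tables 14.4.3, 14.4.4 and 14.4.6 by a repeat no further from Day 7. For the liver thresholds in Table 14.4.7 the consequence is inconsistency between tables, not loss. For hematology, non-liver chemistry and ALT or AST between 1x and 3x ULN, a displaced value would be seen only in non-topline listings unless it was also reported as an AE. That sits poorly with Protocol 9.1.

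The frequency is unknown. A reader might take 46% as the share of patients affected. It is a share of assumed, equally weighted day-pairs, it falls to 24% when repeats run to Day 21, and it says nothing about how many subjects have a repeat at all. The correction is worth making because it is cheap and concerns topline safety tables.

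**What to change.** In SAP 6.3:

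- Build the shift tables on the worst non-missing post-dose value in the on-study window already defined there, scheduled or not. Use the highest value for ALT, AST, ALP, bilirubin, CPK and creatinine. Show lowest and highest separately for analytes that can be abnormal in both directions. If the by-visit shift tables must stay, add worst-value shift tables beside them.
- Keep closest-to-target selection for mean change-from-baseline and other by-visit summaries.
- State the laboratory target date and say which repeat or unscheduled draws belong to the End of Treatment Visit.

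Under a worst-value rule no day-pair in the grids above loses an abnormal first value. The cost is SAP wording, a changed selection flag and possibly a few more tables. No new samples are needed. Abnormality counts may rise slightly, and subjects with more draws have more chances to show an abnormal value, which a footnote can state.

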#### 6.3.1 *Liver Toxicity Evaluation*

Potential drug induced liver injury are those events meeting Hy's Law, defined as:

1. Aminotransferases (AT) ALT or AST elevation > 3 times the upper limit of normal (ULN);
2. Total bilirubin (TBL) > 2 times ULN, without initial findings of cholestasis (elevated serum alkaline phosphatase); and

3. No other immediately apparent possible causes of AT elevation and hyperbilirubinemia, included but not limited to: viral hepatitis, pre-existing chronic or acute liver disease, or the administration of other drug(s) known to be hepatotoxic.

Any potential drug-induced liver injuries (DILIs), meeting the above defined criteria, will be reported as SAEs and tabulated by treatment group. A listing will be prepared that shows the AT and TBL values for all subjects that experience either AT > 3 times the upper limit of normal or TBL > 2 times the upper limit of normal at any time during the study.

Additionally, a table will be created that summarizes the incidence (as the number of subjects experiencing the given measurement post-randomization) of the following:

- >3x, >5x, >10x, and >20x ULN elevations of AST, ALT, and either ALT or AST
- Any elevations of bilirubin >1x ULN and >2x ULN
- Any elevations of ALP > 1.5x ULN
- Elevation of AST or ALT (>3x ULN) accompanied by elevated bilirubin (>1.5x ULN and >2x ULN)
- Elevation of AST or ALT along with an on-study AE of nausea, vomiting, anorexia, abdominal pain, or fatigue

An evaluation of Drug-Induced Serious Hepatotoxicity (eDISH) plot will be created by plotting the maximum total bilirubin against maximum ALT and presenting these data points by treatment group for the current study and the BHV3000-301/302 meta-analysis. The maximum values for each subject during the study will be identified as the maximum values that occur post-baseline, but not necessarily concurrently. Maximum total bilirubin (presented as xULN) will be plotted on a log scale on the y-axis and maximum ALT (presented as xULN) will be plotted on a log scale on the x-axis. A horizontal reference line will be placed at 2x ULN for maximum total bilirubin and a vertical reference line will be placed at 3x ULN for maximum ALT. The lower left quadrant will be labeled “Normal Range”. The upper left quadrant will be labeled “Hyperbilirubinemia”. The lower right quadrant will be labeled “Temple’s Corollary”. The upper right quadrant will be labeled “Possible Hy’s Law Range”.

## **6.4 Physical Examinations**

For each body system, the shift from screening will be summarized as the number and percentage of subjects with each result (normal, abnormal, or physical examination not done) at the end of treatment visit.

### **6.4.1 Vital Signs and Physical Measurements**

The observed value and change from baseline in vital signs will be summarized at baseline and end of treatment.

#### **6.4.2     *Electrocardiogram***

The shift from baseline in ECG parameters will be summarized as the number and percentage of subjects with normal, abnormal, and clinically significant abnormal results at the screening and end of treatment visits. Descriptive statistics for ECG interval data (e.g., RR, QRS, PR, QT, QTcF), and ventricular heart rate will also be reported for the screening and end of treatment visits.

#### **6.5     Concomitant Medications**

Concomitant medications will be coded using the WHO-DD. Results will be tabulated by Anatomic Therapeutic Class (ATC) and PT.

### Appendix 1. BHV3000-301 Tables, Listings, And Figures

Table Number	Title	Population	Topline
14.1.1	Subject Disposition	All Subjects	Y
14.1.2.1	Demographic and Baseline Characteristics	mITT Subjects	Y
14.1.2.2	Demographic and Baseline Characteristics	Subjects Enrolled but Not Randomized	
14.1.2.3	Demographic and Baseline Characteristics	Subjects Randomized but Not Treated	
14.1.2.4	Demographic and Baseline Characteristics	Treated Subjects	
14.1.3	Medical History	Treated Subjects	
14.1.4.1	Migraine Disease History	mITT Subjects	Y
14.1.4.2	Migraine Disease History	Subjects Enrolled but Not Randomized	
14.1.4.3	Migraine Disease History	Subjects Randomized but Not Treated	
14.1.5	Cardiac and Other Risk Factors	Treated Subjects	
14.1.6	Prior Triptan Response	mITT Subjects	
14.1.7	Current Triptan Response	mITT Subjects	
14.1.8	Subgroup Summary	mITT Subjects	Y
14.1.9.1	Missing Data Summary	Randomized Subjects	
14.1.9.2	Missing Pain Data Summary by Subgroup	mITT Subjects	
14.2.1	Pain Freedom at 2 Hours Post Dose: Observed Data	mITT Subjects	
14.2.1.1	Pain Freedom at 2 Hours Post Dose: Asian Subjects Only	mITT Subjects	
14.2.1.2	Pain Freedom at 2 Hours Post Dose: Primary Analysis	mITT Subjects	Y
14.2.1.2.1	Pain Freedom at 2 Hours Post Dose: Subgroup Analysis by Age	mITT Subjects	
14.2.1.2.2	Pain Freedom at 2 Hours Post Dose: Subgroup Analysis by Race	mITT Subjects	
14.2.1.2.3	Pain Freedom at 2 Hours Post Dose: Subgroup Analysis by Sex	mITT Subjects	
14.2.1.2.4	Pain Freedom at 2 Hours Post Dose: Subgroup Analysis by Aura	mITT Subjects	
14.2.1.2.5	Pain Freedom at 2 Hours Post Dose: Subgroup Analysis by Headaches per Month	mITT Subjects	
14.2.1.2.6	Pain Freedom at 2 Hours Post Dose: Subgroup Analysis by Prior Triptan Response	mITT Subjects	
14.2.1.2.7	Pain Freedom at 2 Hours Post Dose: Subgroup Analysis by Cardiovascular Risk	mITT Subjects	
14.2.1.3.1	Pain Freedom at 2 Hours Post Dose: Sensitivity Analysis 1	mITT Subjects	
14.2.1.3.2	Pain Freedom at 2 Hours Post Dose: Sensitivity Analysis 2	mITT Subjects	
14.2.1.3.3	Pain Freedom at 2 Hours Post Dose: Sensitivity Analysis 3	mITT Subjects	
14.2.1.3.4	Pain Freedom at 2 Hours Post Dose: Sensitivity Analysis 4	mITT Subjects	
14.2.1.3.5	Pain Freedom at 2 Hours Post Dose: Sensitivity Analysis 5	mITT Subjects	

Table Number	Title	Population	Topline
14.2.2	Most Bothersome Symptom at Migraine Onset: Observed Data	mITT Subjects	
14.2.2.1	Historically Most Bothersome Symptom versus Most Bothersome Symptom at Migraine Onset	mITT Subjects	
14.2.2.2	Freedom from Most Bothersome Symptom at 2 Hours Post Dose: Primary Analysis	mITT Subjects	Y
14.2.2.2.1	Freedom from Most Bothersome Symptom at 2 Hours Post Dose: Subgroup Analysis by Age	mITT Subjects	
14.2.2.2.2	Freedom from Most Bothersome Symptom at 2 Hours Post Dose: Subgroup Analysis by Race	mITT Subjects	
14.2.2.2.3	Freedom from Most Bothersome Symptom at 2 Hours Post Dose: Subgroup Analysis by Sex	mITT Subjects	
14.2.2.2.4	Freedom from Most Bothersome Symptom at 2 Hours Post Dose: Subgroup Analysis by Aura	mITT Subjects	
14.2.2.2.5	Freedom from Most Bothersome Symptom at 2 Hours Post Dose: Subgroup Analysis by Headaches per Month	mITT Subjects	
14.2.2.2.6	Freedom from Most Bothersome Symptom at 2 Hours Post Dose: Subgroup Analysis by Prior Triptan Response	mITT Subjects	
14.2.2.2.7	Freedom from Most Bothersome Symptom at 2 Hours Post Dose: Subgroup Analysis by Cardiovascular Risk	mITT Subjects	
14.2.2.3.1	Freedom from Most Bothersome Symptom at 2 Hours Post Dose: Sensitivity Analysis 1	mITT Subjects	
14.2.2.3.2	Freedom from Most Bothersome Symptom at 2 Hours Post Dose: Sensitivity Analysis 2	mITT Subjects	
14.2.2.3.3	Freedom from Most Bothersome Symptom at 2 Hours Post Dose: Sensitivity Analysis 3	mITT Subjects	
14.2.2.3.4	Freedom from Most Bothersome Symptom at 2 Hours Post Dose: Sensitivity Analysis 4	mITT Subjects	
14.2.2.3.5	Freedom from Most Bothersome Symptom at 2 Hours Post Dose: Sensitivity Analysis 5	mITT Subjects	
14.2.2.3.6	Freedom from Most Bothersome Symptom at 2 Hours Post Dose: Sensitivity Analysis 6	mITT Subjects	
14.2.3.1	Most Bothersome Symptom Score at 2 Hours Post Dose: Observed Data	mITT Subjects	
14.2.3.1.1	Freedom from Photophobia at 2 Hours Post Dose in Subjects who Reported Photophobia at Study Migraine Onset: Observed Data	mITT Subjects	
14.2.3.1.2	Freedom from Photophobia at 2 Hours Post Dose in Subjects who Reported Photophobia at Study Migraine Onset: Secondary Analysis	mITT Subjects	Y
14.2.3.2.1	Freedom from Phonophobia at 2 Hours Post Dose in Subjects who Reported Phonophobia at Study Migraine Onset: Observed Data	mITT Subjects	
14.2.3.2.2	Freedom from Phonophobia at 2 Hours Post Dose in Subjects who Reported Phonophobia at Study Migraine Onset: Secondary Analysis	mITT Subjects	Y
14.2.3.3.1	Pain Relief at 2 Hours Post Dose: Observed Data	mITT Subjects	
14.2.3.3.2	Pain Relief at 2 Hours Post Dose: Secondary Analysis	mITT Subjects	Y

Table Number	Title	Population	Topline
14.2.3.4.1	Freedom from Nausea at 2 Hours Post Dose in Subjects who Reported Nausea at Study Migraine Onset: Observed Data	mITT Subjects	
14.2.3.4.2	Freedom from Nausea at 2 Hours Post Dose in Subjects who Reported Nausea at Study Migraine Onset: Secondary Analysis	mITT Subjects	Y
14.2.3.5	Rescue Medication within 24 Hours Post Dose: Secondary Analysis	mITT Subjects	
14.2.3.6.1	Functional Disability Scale at 2 Hours Post Dose: Observed Data	mITT Subjects	
14.2.3.6.2	Functional Disability Scale at 2 Hours Post Dose: Secondary Analysis	mITT Subjects	
14.2.3.7.1	Sustained Pain Freedom from 2 to 24 Hours Post Dose: Secondary Analysis	mITT Subjects	
14.2.3.7.2	Sustained Pain Relief from 2 to 24 Hours Post Dose: Secondary Analysis	mITT Subjects	
14.2.3.7.3	Sustained Pain Freedom from 2 to 48 Hours Post Dose: Secondary Analysis	mITT Subjects	
14.2.3.7.4	Sustained Pain Relief from 2 to 48 Hours Post Dose: Secondary Analysis	mITT Subjects	
14.2.3.7.5	Pain Relapse from 2 to 48 Hours Post Dose: Secondary Analysis	mITT Subjects	
14.2.3.8.1	Functional Disability Scale at 24 Hours Post Dose: Exploratory Analysis	mITT Subjects	
14.2.3.8.2	Pain Relief at 30, 60, and 90 Minutes Post Dose: Exploratory Analysis	mITT Subjects	
14.2.3.8.3	Kaplan-Meier Time to Pain Relief: Exploratory Analysis	mITT Subjects	Y
14.2.3.8.4	Median Time to Pain Relief	mITT Subjects	Y
14.2.3.8.5	Preference of Medication at 24 Hours Post Dose: Exploratory Analysis	mITT Subjects	
14.2.3.8.6.1	Migraine Quality of Life Questionnaire at 24 Hours Post Dose: Continuous Exploratory Analysis	mITT Subjects	
14.2.3.8.6.2	Migraine Quality of Life Questionnaire at 24 Hours Post Dose: Frequency Exploratory Analysis	mITT Subjects	
14.2.3.8.7	Pain Freedom at Every Timepoint Post Dose: Exploratory Analysis	mITT Subjects	
14.2.3.8.8	Pain Relief at Every Timepoint Post Dose: Exploratory Analysis	mITT Subjects	
14.2.3.8.9	Freedom from Most Bothersome Symptom at Every Timepoint Post Dose: Exploratory Analysis	mITT Subjects	
14.2.3.8.9.1	Freedom from Photophobia at Every Timepoint Post Dose: Exploratory Analysis	mITT Subjects	
14.2.3.8.9.2	Freedom from Phonophobia at Every Timepoint Post Dose: Exploratory Analysis	mITT Subjects	
14.2.3.8.9.3	Freedom from Nausea at Every Timepoint Post Dose: Exploratory Analysis	mITT Subjects	
14.2.3.8.10	Functional Disability Scale at Every Timepoint Post Dose: Exploratory Analysis	mITT Subjects	

Table Number	Title	Population	Topline
14.2.3.8.11	Sheehan-Suicidality Tracking Scale: Exploratory Analysis	mITT Subjects	
14.2.3.9.1	Kaplan-Meier Time to Pain Freedom: Exploratory Analysis	mITT Subjects	Y
14.2.3.9.2	Median Time to Pain Freedom	mITT Subjects	Y
14.3.1.1	Self-Reported Exposure Data Summary	All Randomized Subjects	
14.3.1.2	Drug Accountability Data Summary	All Randomized Subjects	
14.3.1.3	Cross Tabulation of Exposure and Accountability Data	All Randomized Subjects	
14.3.2.1	Summary of On-Study Adverse Events	Treated Subjects	Y
14.3.2.2	Incidence of On-study Adverse Events by System Organ Class and Preferred Term	Treated Subjects	Y
14.3.2.3	Incidence of On-study Adverse Events Related to Study Drug by System Organ Class and Preferred Term	Treated Subjects	
14.3.2.4	Incidence of On-study Serious Adverse Events by System Organ Class and Preferred Term	Treated Subjects	Y
14.3.2.5	Incidence of On-study Adverse Events with Severe Grade by System Organ Class and Preferred Term	Treated Subjects	
14.4.1.1	Hematology (SI Units): Observed and Change From Baseline Values by Visit	Treated Subjects	
14.4.1.2	Hematology (UI Units): Observed and Change From Baseline Values by Visit	Treated Subjects	
14.4.2.1	Serum Chemistry (SI Units): Observed and Change From Baseline Values by Visit	Treated Subjects	
14.4.2.2	Serum Chemistry (US Units): Observed and Change From Baseline Values by Visit	Treated Subjects	
14.4.3.1	Hematology (SI Units): Shift from Baseline by Visit	Treated Subjects	Y
14.4.3.2	Hematology (US Units): Shift from Baseline by Visit	Treated Subjects	Y
14.4.4.1	Serum Chemistry (SI Units): Shift from Baseline by Visit	Treated Subjects	Y
14.4.4.2	Serum Chemistry (US Units): Shift from Baseline by Visit	Treated Subjects	Y
14.4.5.1	Urinalysis (SI Units): Shift from Baseline by Visit	Treated Subjects	
14.4.5.2	Urinalysis (SI Units): Shift from Baseline by Visit	Treated Subjects	
14.4.6.1	Transaminases (SI Units): Shift from Baseline by Visit	Treated Subjects	Y
14.4.6.2	Transaminases (SI Units): Shift from Baseline by Visit	Treated Subjects	Y
14.4.7	Summary of On-Study Liver Toxicity	Treated Subjects	Y
14.5.1	Vital Signs and Physical Measurements: Observed and Change from Baseline Values by Visit	Treated Subjects	
14.5.2.1	Electrocardiogram: Observed and Change from Baseline Values by Visit	Treated Subjects	
14.5.2.2	Electrocardiogram: Shift from Baseline by Visit	Treated Subjects	

Table Number	Title	Population	Topline
14.5.3.1	Concomitant Medications by Therapeutic Class and Preferred Term	Treated Subjects	
14.5.3.2	Rescue Medications by Therapeutic Class and Preferred Term	Treated Subjects	

Listing Number	Title	Population	Topline
16.2.1	Subject Disposition	All Subjects	
16.2.2	Subject Eligibility	All Subjects	
16.2.3	Protocol Deviations	All Subjects	
16.2.4.1	Demographic and Baseline Characteristics	All Subjects	
16.2.4.2	Significant Medical History	All Subjects	
16.2.4.3	General Migrain Disease History	All Subjects	
16.2.4.3.1	Migraine Symptom History	All Subjects	
16.2.4.3.1	Migraine Aura Symptom History	All Subjects	
16.2.5	Batch Numbers	All Subjects	
16.2.6	Subpopulations and Subgroups	All Subjects	
16.2.7.1	Observed Pain and MBS Efficacy Measurements	mITT Subjects	
16.2.7.2	Observed Primary Efficacy Measurements at 2 Hours Post Dose	mITT Subjects	
16.2.7.3	Fuinctional Disability Scale	mITT Subjects	
16.2.7.4	Preference of Medication at 24 Hours Post Dose	mITT Subjects	
16.2.7.5	Migraine Quality of Life Questionnaire at 24 Hours Post Dose	mITT Subjects	
16.2.8	Exposure and Accountability Data	mITT Subjects	
16.2.9.1	Pre-Randomization Adverse Events	All Subjects	
16.2.9.2	On-Study Advserse Events	All Subjects	
16.2.9.3	Serious On-Study Adverse Events	All Subjects	
16.2.9.4	Deaths	All Subjects	
16.2.10.1.1	Hematology Results (SI Units)	All Subjects	
16.2.10.1.2	Hematology Results (US Units)	All Subjects	
16.2.10.2.1	Serum Chemistry Results (SI Units)	All Subjects	
16.2.10.2.2	Serum Chemistry Results (US Units)	All Subjects	
16.2.10.3.1	Urinalysis Results (SI Units)	All Subjects	
16.2.10.3.2	Urinalysis Results (US Units)	All Subjects	
16.2.10.4.1	Endocrine Results (SI Units)	All Subjects	
16.2.10.4.2	Endocrine Results (US Units)	All Subjects	
16.2.10.5.1	Pregnancy Results (SI Units)	All Subjects	
16.2.10.5.2	Pregnancy Results (US Units)	All Subjects	

Listing Number	Title	Population	Topline
16.2.10.6	GC/MS Results	All Subjects	
16.2.10.7.1	All Abnormal Laboratory Results (SI Units)	All Subjects	
16.2.10.7.2	All Abnormal Laboratory Results (US Units)	All Subjects	
16.2.10.8.1	Potential Drug Induced Liver Injury (SI Units)	All Subjects	Y
16.2.10.8.2	Potential Drug Induced Liver Injury (US Units)	All Subjects	Y
16.2.11.1	Vital Signs and Physical Measurements	All Subjects	
16.2.11.2	Electrocardiogram Results	All Subjects	
16.2.11.3.1	Comcomitant Medications	All Subjects	
16.2.11.3.2	Prophylactic Migraine Medications	All Subjects	
16.2.11.3.3	Rescue Medications	All Subjects	
16.2.11.4.1	Prior Triptan Response	All Subjects	
16.2.11.4.2	Current Triptan Response	All Subjects	
16.2.11.5	Procedures	All Subjects	
16.2.11.6	Sheehan-Suicidality Tracking Scale Results	All Subjects	
16.2.11.7	Cardiac and all Other Risk Factors	All Subjects	

Figure Number	Title	Population	Topline
14.2.1	Forest Plot of Pain Freedom at 2 Hours Post Dose	mITT Subjects	
14.2.1.1	Forest Plot of Pain Freedom at 2 Hours Post Dose: Sensitivity Analysis 1	mITT Subjects	
14.2.1.2	Forest Plot of Pain Freedom at 2 Hours Post Dose: Sensitivity Analysis 2	mITT Subjects	
14.2.1.3	Forest Plot of Pain Freedom at 2 Hours Post Dose: Sensitivity Analysis 3	mITT Subjects	
14.2.1.4	Forest Plot of Pain Freedom at 2 Hours Post Dose: Sensitivity Analysis 4	mITT Subjects	
14.2.1.5	Forest Plot of Pain Freedom at 2 Hours Post Dose: Sensitivity Analysis 5	mITT Subjects	
14.2.1.6	Forest Plot of Pain Freedom at 2 Hours Post Dose by Subgroup	mITT Subjects	
14.2.2	Forest Plot of Freedom from Most Bothersome Symptom at 2 Hours Post Dose	mITT Subjects	
14.2.2.1	Forest Plot of Freedom from Most Bothersome Symptom at 2 Hours Post Dose: Sensitivity Analysis 1	mITT Subjects	
14.2.2.2	Forest Plot of Freedom from Most Bothersome Symptom at 2 Hours Post Dose: Sensitivity Analysis 2	mITT Subjects	

Figure Number	Title	Population	Topline
14.2.2.3	Forest Plot of Freedom from Most Bothersome Symptom at 2 Hours Post Dose: Sensitivity Analysis 3	mITT Subjects	
14.2.2.4	Forest Plot of Freedom from Most Bothersome Symptom at 2 Hours Post Dose: Sensitivity Analysis 4	mITT Subjects	
14.2.2.5	Forest Plot of Freedom from Most Bothersome Symptom at 2 Hours Post Dose: Sensitivity Analysis 5	mITT Subjects	
14.2.2.6	Forest Plot of Freedom from Most Bothersome Symptom at 2 Hours Post Dose: Sensitivity Analysis 6	mITT Subjects	
14.2.2.7	Forest Plot of Freedom from Most Bothersome Symptom at 2 Hours Post Dose by Subgroup	mITT Subjects	
14.2.3	Forest Plot of Freedom from Photophobia, Phonophobia, and Nausea at 2 Hours Post Dose	mITT Subjects	
14.2.4	Forest Plot of Pain Relief at 2 Hours Post Dose	mITT Subjects	
14.2.5	Forest Plot of Probability of Requiring Rescue Medication within 24 Hour Post Dose	mITT Subjects	
14.2.6	Forest Plot of Probability of Functioning Normally According to the Functional Disability Scale at 2 Hour Post Dose	mITT Subjects	
14.2.7	Forest Plot of Durability of Pain Relief or Pain Freedom	mITT Subjects	
14.2.8	Forest Plot of Probability of Pain Relapse	mITT Subjects	
14.2.9	Forest Plot of Probability of Functioning Normally According to the Functional Disability Scale at 24 Hour Post Dose	mITT Subjects	
14.2.10	Forest Plot of Pain Relief at 30, 60, and 90 Minutes Post Dose	mITT Subjects	
14.2.11	Kaplan-Meier Plot of Time to Pain Relief to Two Hours Post Dose	mITT Subjects	Y
14.2.12	Kaplan-Meier Plot of Time to Pain Freedom to Eight Hours Post Dose	mITT Subjects	Y
14.3.1	Evaluation of Drug-Induced Hepatotoxicity (eDISH)	Treated Subjects	Y

